7.1.2.4 Immunogenicity values

If antibody titers and concentrations are below the cutoff, i.e the result is of the form ‘<xx’, the value will be set to $0.5 * xx$ before performing GMT calculations. Only samples for which PBMC preparation was performed within 8 hours will be used for analysis.

“Below LOD” in IFN- γ and IL-4 data should be considered as “0”.

“NR” in IFN- γ and IL-4 data should be considered as “not reportable” results.

Value of “< 100” and “IR” in Nab data due to hemolyzed samples should be considered as “not reportable” results.

“>ULOQ” in Nab data are results above ULOQ at the maximal dilution and the “>ULOQ” value should be assigned as “64000”.

7.1.3 Safety Assessments

7.1.3.1 Adverse Events

Immediate AEs are defined as any solicited local and systemic AEs and unsolicited AEs occurring within 30 minutes after vaccination. Multiple occurrences of the same event within a subject will be counted once in the maximum severity of symptoms category (potentially life threatening > severe > moderate > mild). Related is defined as AEs with a causality of “Definitely Related”, “Probably Related” or “Possibly Related”. Not related is defined as AEs with a causality of “Probably Not Related” or “Definitely Not Related”.

Adverse events will be coded according to the MedDRA version 24.1.

(1) Duration of Adverse Events

Duration of Adverse Events (days) = AE stop date – AE start date + 1

7.1.3.1.1 Solicited Adverse Events

The PI assessment of a solicited adverse event will always be used when available.

In the event that both an e-diary and a paper diary were completed by the subject for the same solicited AE and the same timepoint, the record with the PI assessment will be used for analysis; otherwise, the paper diary data will be used in the analysis.

Scheduled day and timepoint, if applicable, will be used as record identifier(s) in solicited AE summaries.

7.1.3.1.1 Serious Adverse Events (SAE)

An SAE is any untoward medical occurrence (whether or not considered to be related to the study vaccine) that, at any dose:

- Results in death
- Is life-threatening (at the time of the event)
- Requires inpatient hospitalization (≥ 24 hours) or prolongation of existing hospitalization (elective hospitalizations/procedures for pre-existing conditions that have not worsened are excluded)
- Results in persistent or significant disability/incapacity
- Is a congenital abnormality/birth defect

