12 ASSURANCE OF SUBJECT SAFETY

12.1 Definitions

12.1.1 Serious Adverse Events

An SAE is any untoward medical occurrence (whether or not considered to be related to the study vaccine) that, at any dose:

- ◆ Results in death;
- ◆ Is life-threatening (at the time of the event);

Note: the term “life-threatening” in the definition of an SAE refers to an event that put the subject at risk of death at the time of the event; it does not refer to an event that hypothetically might have caused death if it were more severe;

- ◆ Requires inpatient hospitalization (≥ 24 hours) or prolongation of existing hospitalization (elective hospitalizations/procedures for pre-existing conditions that have not worsened are excluded);
- ◆ Results in persistent or significant disability/incapacity;
- ◆ Is a congenital abnormality/birth defect;
- ◆ Is another medically important event.

Medical and scientific judgment should be exercised in deciding whether expedited reporting is appropriate in other situations, such as important medical events that may not be immediately life-threatening or result in death or hospitalization but that may jeopardize the subject’s health or may require an intervention to prevent one of the other outcomes listed in the definition above. These events should be considered serious. Examples of such events are intensive treatment in an emergency room for allergic bronchospasm, blood dyscrasias, or convulsions that do not result in hospitalization or the development of drug dependency or drug abuse. See Section 12.1.6 for initial SAE reporting by the Investigator.

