12.1.2 Adverse Events

An AE or adverse experience is defined as any untoward medical occurrence in a subject or clinical investigation subject who was administered a pharmaceutical product, with or without a causal relationship with the treatment. An AE can be any unfavorable and unintended sign, symptom, or disease temporally associated with the use of a medicinal product, whether or not related to a medicinal product.

Information such as the date and time of onset and resolution (duration), intensity (defined below), seriousness, any required treatment or action taken, outcome, relationship to the investigational vaccine, and whether the AE caused withdrawal from the study will be collected.

The intensity of all AEs will be graded as mild (1), moderate (2) severe (3), or potentially life threatening (4), according to the FDA Guidance for Industry: Toxicity Grading Scale for Healthy Adult and Adolescent Volunteers Enrolled in Preventive Vaccine Clinical Trials [FDA 2007] for the events covered in the guidance and the following definitions for all other events:

Mild (Grade 1):	The AE is easily tolerated and does not interfere with usual activity;
Moderate (Grade 2):	The AE interferes with daily activity, but the subject is still able to function;
Severe (Grade 3):	The AE is incapacitating and the subject is unable to work or complete usual activity;
Potentially life-threatening (Grade 4):	The AE is likely to be life-threatening if not treated in a timely manner.

Note: According to the FDA Guidance for Industry: Toxicity Grading Scale for Healthy Adult and Adolescent Volunteers Enrolled in Preventive Vaccine Clinical Trials [FDA 2007]: *“Nonetheless, we believe that categorization or grading of data as outlined in this document is supplementary to and should not replace full and complete data analysis. These guidelines for toxicity grading scales are primarily intended for healthy adult and adolescent volunteers.”* and *“Toxicity grading scales for laboratory abnormalities should consider the local laboratory reference values when the parameter limit values are defined. The characterization of laboratory parameters among some populations of healthy adults and adolescents may require the exercise of clinical judgment, for example, consideration of the potential for ethnic differences in white blood cell (WBC) counts or gender differences in creatine phosphokinase (CPK) values.”*

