1 INTRODUCTION

This statistical analysis plan (SAP) is based on the final protocol (v3.0) dated 16-NOV-2021. The plan covers statistical analysis, tabulations and listings of the study data to assess the safety and immunogenicity of MT-2766.

Any statistical analysis details described in this document supersede any description of statistical analysis in the protocol.

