2.2 Study Endpoint(s)

2.2.1 Primary Endpoints

The following primary immunogenicity and safety endpoints are for Groups 1 (3.75 µg of MT-2766) and Group 2 (placebo for MT-2766 3.75 µg).

Safety:

1. The incidences, severity, and investigator-assessed causality of immediate adverse events (AEs) that occur within 30 minutes of first (Day 0) and second (Day 21) injections.
2. The incidences and severity of the following solicited AEs that develop within 7 days of first (Day 0) and second (Day 21) injections: (i) local AEs (injection site erythema, injection site swelling, injection site induration, and injection site pain) and (ii) systemic AEs (fever, headache, fatigue, muscle aches, joint aches, chills, a feeling of general discomfort, swelling in the axilla, and swelling in the neck).
3. The incidences, severity, and investigator-assessed causality of unsolicited AEs that develop within 21 days of first (Day 0) and second (Day 21) injections.
4. The incidences of serious AEs (SAEs), medically attended AEs (MAAEs), AEs leading to withdrawal, AEs of special interest (AESIs), and deaths up to 21 days following first (Day 0) and second (Day 21) injections. AESIs include vaccine-associated enhanced diseases (VAED), hypersensitivity reactions, and potential immune-mediated diseases (pIMDs).

Immunogenicity:

1. SARS-CoV-2 neutralizing antibody (Nab) responses will be analyzed on Days 0, 21, and 42 using the following parameters: geometric mean antibody titer (GMT), seroconversion (SC) rate, and geometric mean fold rise (GMFR);
2. SARS-CoV-2-specific T helper 1 (Th1) cell-mediated immune (CMI) responses will be measured on Days 0, 21, and 42 using the interferon (IFN)- γ enzyme-linked immunospot (ELISpot) assay;
3. SARS-CoV-2-specific T helper 2 (Th2) CMI responses will be measured on Days 0, 21, and 42 using the interleukin (IL)-4 ELISpot assay.

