2.2.2 Secondary Endpoints

The following secondary safety and immunogenicity endpoints are for Groups 1 and Group 2.

Safety:

1. The incidences of SAEs, MAAEs, AEs leading to withdrawal, AESIs, and deaths from Day 43 to Day 201;
2. The incidences of SAEs, MAAEs, AEs leading to withdrawal, AESIs, and deaths from Day 202 to Day 386;
3. The numbers and percentages of subjects with normal and abnormal urine, hematological, and biochemical test results within three days of first (Day 0) and second (Day 21) injections.

Immunogenicity:

1. Persistence of SARS-CoV-2 Nab response will be assessed on Days 128, 201, and 386 using the following parameters: GMT, SC rate, and GMFR.
2. SARS-CoV-2-specific antibody responses will be measured on Days 0, 21, and 42 based on the total immunoglobulin G (IgG) level, and the persistence of these antibodies will be analyzed on Days 128, 201, and 386 using the following parameters: GMT, SC rate, and GMFR;
3. SARS-CoV-2-specific Th1 CMI responses will be measured on Days 201 and 386 using the IFN- γ ELISpot assay;
4. SARS-CoV-2-specific Th2 CMI responses will be measured on Days 201 and 386 using the IL-4 ELISpot assay;

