7 DATA CONVENTIONS

7.1 Analysis Variable Definitions

7.1.1 Study Subjects

7.1.1.1 Demographic and Other Baseline Characteristics

BMI will be recalculated to 1 decimal place using the following formula:

$$\text{BMI (kg/m}^2\text{)} = \text{weight at screening (kg)} / \{\text{height at screening (m)}\}^2$$

Significant comorbidities will be defined as co-morbid conditions that puts them at higher risk for severe COVID-19 disease. These significant comorbidities include obesity, hypertension, type 1 or type 2 diabetes, chronic obstructive pulmonary disease (COPD), cardiovascular diseases, chronic kidney diseases, or be immunocompromised persons (e.g., treatment-controlled HIV infection, organ transplant recipients, or patients receiving cancer chemotherapy).

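### The SAP's definition of a serious adverse event leaves out the protocol's medically-important-event criterion and does not declare the change

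*SAP*

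**What the plan says.** Protocol 12.1.1 lists six criteria for an SAE, ending with "Is another medically important event". The paragraph after the list explains that criterion. It covers events that may put the subject's health at risk, or need intervention to avoid one of the listed outcomes, even without death, immediate threat to life or admission. Of these it says "These events should be considered serious". Its examples include intensive emergency-room treatment for allergic bronchospasm, blood dyscrasias, and convulsions that do not lead to admission.

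The SAP uses the number 7.1.3.1.1 twice; the section at issue is the second, on SAEs. It falls under "7.1 Analysis Variable Definitions" and gives five criteria, the last being "Is a congenital abnormality/birth defect". The sixth criterion appears nowhere else in the SAP.

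SAP Section 1 states: "Any statistical analysis details described in this document supersede any description of statistical analysis in the protocol".

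The SAE count feeds primary safety endpoint 4 (SAP 2.2.1: "The incidences of serious AEs (SAEs), medically attended AEs (MAAEs), AEs leading to withdrawal, AEs of special interest (AESIs), and deaths up to 21 days" after each injection) and the first two secondary safety endpoints (SAP 2.2.2; the first reads "The incidences of SAEs, MAAEs, AEs leading to withdrawal, AESIs, and deaths from Day 43 to Day 201"). SAP 8.3.2 gives SAEs and related SAEs their own rows in both overall summaries, and 8.3.2.2 tabulates SAEs by system organ class and preferred term.

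SAP Section 10, on changes from the protocol, mentions only that Group 3 was not enrolled and that, because the study was discontinued, Day 386 and some other items were not measured.

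**The concern.** The two documents define the same safety variable differently, and the narrower definition sits where the SAP says what will be analysed. Protocol 12.1.6 (reporting) and the pause rule for related SAEs in 12.1.11 both rely on the protocol's definition. On a literal reading of the SAP, an event could be reported within 24 hours as an SAE, and even prompt a pause, yet be absent from the SAE tables.

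The missing criterion is relevant to this product. Protocol 12.1.4.1.2 names severe allergic reactions as an important potential risk of plant-based production. The admission criterion requires at least 24 hours in hospital. A reaction treated intensively in an emergency room, without admission and without immediate threat to life, would ordinarily be serious only through the sixth criterion. Protocol 11.1.7 also treats spontaneous abortion as an SAE in every case, and none of the SAP's five criteria names it.

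**Working it through.** **1. Comparison of the criteria.**

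| Criterion | Protocol 12.1.1 | SAP 7.1.3.1.1 (SAE) |
|---|---|---|
| Death | yes | yes |
| Life-threatening | yes | yes |
| Admission of 24 hours or more, or prolonged stay | yes | yes |
| Lasting or significant disability | yes | yes |
| Congenital abnormality | yes | yes |
| Medically important event | yes | **no** |

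Six against five: five match and one is missing. The SAP also leaves out the protocol's note on what life-threatening means and its paragraph on medical judgment.

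**2. Which outputs are affected.** On a literal reading: the SAE and related-SAE rows for each Day 0–21 period and up to end of study, and the SAE table by system organ class and preferred term.

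**3. Where an omitted event would still be seen.** SAP 7.1.3.1.2 counts any event needing an emergency-room visit or a visit to a health care provider as medically attended. Under SAP 7.1.3.1.3.2, related hypersensitivity events are of special interest, and Appendix 3 lists bronchospasm. Both categories belong to primary safety endpoint 4 alongside SAEs. Coverage is partial: convulsion is not on the term lists in Appendices 2 to 4, so a convulsion without admission would normally be seen only as a medically attended event. All safety data are also listed (SAP 8.3).

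**4. Which source the tables would use.** Protocol 12.1.2 has the site record, for each event, items that include "intensity (defined below), seriousness, any required treatment or action taken, outcome". The SAP does not say whether its SAE tables use that record or apply its own five criteria. It does name the source for other variables: investigator causality categories for relatedness (7.1.3.1) and the investigator's assessment for solicited events.

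**5. Size.** The plan states no figure to reproduce, and gives neither an SAE rate nor the share of SAEs that are serious only by medical importance. The undercount therefore cannot be computed. To show how coarse the counts are, assume all 100 planned Group 1 subjects are dosed and take the exact (Clopper-Pearson) two-sided 95% upper bound, the value of p at which P(X ≤ x) = 0.025 for X binomial with n = 100:

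- x = 0: (1 − p)^100 = 0.025, so p = 1 − 0.025^(1/100) = 3.6%.
- x = 1: (1 − p)^100 + 100p(1 − p)^99 = 0.025, so p = 5.4%.
- x = 2: adding 4950p²(1 − p)^98 to the left side gives p = 7.0%.

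The event counts are assumptions, not estimates from the documents.

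**The case against.** The strongest reply is that the shortened list has no effect in practice. The investigator classifies seriousness under the protocol, and the SAP contains no algorithm for re-deriving it and no rule for overriding it. If the tables simply use the recorded classification, medically important events are counted. The accompanying omissions and the silence of Section 10 also look more like an incomplete copy than a deliberate change. All of this stands as a reason not to claim that an undercount will occur. It does not make the text right: the only rule the SAP states for this variable is the five-item list.

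Three stronger readings are tempting, and the documents do not support them.

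- A reader might infer from Section 1 that the SAP replaces the protocol's SAE definition altogether. The clause covers only descriptions of statistical analysis. The protocol's are in its Section 14, while the SAE definition is in Section 12. Collection and reporting stay on six criteria. The clause matters only because the SAP puts its own list among the analysis variables.
- A reader might infer that a severe allergic reaction treated in an emergency room would disappear from the safety results. It would still be a medically attended event and, if related, a hypersensitivity event of special interest. If it was life-threatening at the time, it would remain an SAE under the SAP. What could be lost is its place in the SAE rows and table.
- A reader might take the move from 3.6% to 5.4% as the effect on the trial's conclusion. It rests on an assumed omitted event, and SAP 8.3.1.3 plans only descriptive summaries of SAEs, with no test or threshold.

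**Conclusion.** The point holds as an undeclared inconsistency in the definition of a primary safety variable. The SAP gives five of the protocol's six SAE criteria in the place where analysis variables are defined. If that list is applied literally, events serious only by medical importance are left out of the SAE and related-SAE rows and the SAE table, though some remain visible under other categories and all remain in the listings. If the investigator's recorded seriousness is used instead, nothing is lost; the SAP does not say which applies. The omission itself is certain from the text. An actual undercount is not shown, and its size cannot be derived. The bounds of 3.6%, 5.4% and 7.0% depend on 100 dosed vaccinees and assumed counts of 0, 1 and 2, and show only that one or two events are visible in a group of this size.

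**What to change.** Either restore "Is another medically important event" as the sixth criterion in the SAE section of SAP 7.1.3.1.1, or state there that SAEs for analysis are all events recorded as serious by the investigator in the eCRF under protocol 12.1.1. The second option also settles which source the tables use. If the narrower definition is intended, declare and justify it in SAP Section 10. If the final lock has already passed, protocol 14.5 calls for a change of analysis method to be described in the clinical study report; confirm there which definition the SAE tables used.

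The cost is one line of SAP text. No new data are needed, because seriousness is already collected, and no trial procedure changes.

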7.1.3.1.2 Medically Attended Adverse Events (MAAE)

Medically attended adverse events are defined as symptoms or illnesses requiring hospitalization, or emergency room visit, or visit to/by a health care provider.

7.1.3.1.3 Adverse Events of Special Interest (AESI)

7.1.3.1.3.1 Vaccine Associated Enhanced Disease (VAED)

Safety signal of VAED after exposure to the CoVLP formulation will be closely monitored and assessed by retrieving data for this AESI as follows: AEs within the system organ class (SOC): immune system disorders and high level group term (HLGT): lower respiratory tract disorders (excluding obstruction and infection), cardiac disorders, signs and symptoms not elsewhere classified, vascular disorders, heart failures, arteriosclerosis, stenosis, vascular insufficiency and necrosis, cardiac arrhythmias, myocardial disorders, and vascular hemorrhagic disorders. High level term (HLT): renal failure and impairment and preferred term (PT): pericarditis, coagulopathy, deep vein thrombosis, pulmonary embolism, cerebrovascular accidents, peripheral ischemia, liver injury, Guillain-Barre syndrome, anosmia, ageusia, encephalitis, chilblains, vasculitis, erythema multiforme that require inpatient hospitalization (≥ 24 hours) and have laboratory confirmed SARS-CoV-2 infection will be monitored for assessment of any

potential case of VAED. As this list can be updated during the study, any further changes to the AESI terms will be updated in the Signal Management Plan (SMP).

VAED list is attached in the Appendix.

7.1.3.1.3.2 Hypersensitivity Reactions (Anaphylaxis and Severe Allergic Reactions)

All reported events will also be monitored for related hypersensitivity reactions after exposure to the CoVLP formulation. Hypersensitivity will be identified using SMQ broad and narrow terms.

Hypersensitivity reaction list is attached in the Appendix.

7.1.3.1.3.3 Potential Immune-Mediated Diseases (pIMD)

Potential immune-mediated diseases (pIMDs) are a subset of AEs associated to the adjuvant that include autoimmune diseases and other inflammatory and/or neurologic disorders of interest which may or may not have an autoimmune aetiology. pIMDs will be identified using SMQ terms.

pIMD list is attached in the Appendix.

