11.1.3 SARS-CoV-2 Positive Reports

Confirmed COVID-19 cases will be recorded as AEs. Also, confirmed COVID-19 cases will be reported according to the process for reporting SAEs, in the event such case may meet the definition of an SAE. Any potential COVID-19 case that is not a confirmed event and does meet the criteria for an SAE will be reported. The Investigator must report the SAE to MTPC within 24 hours (see Section 12.1.6) of becoming or being made aware.

Following the first vaccination, each subject will be asked to report symptoms associated with COVID-19 during the study. COVID-19 will be defined as the presence of a laboratory-confirmed (virologic method) SARS-CoV-2 infection with the occurrence of a new onset of one or more of the following symptoms:

- ◆ Fever or chills;
- ◆ Cough;
- ◆ Shortness of breath or difficulty breathing;
- ◆ Fatigue;
- ◆ Muscle or body aches;
- ◆ Headache;
- ◆ New loss of taste or smell;
- ◆ Sore throat;
- ◆ Congestion or runny nose;
- ◆ Nausea or vomiting;
- ◆ Diarrhea.

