12.1.4 Adverse Events of Special Interest

12.1.4.1 Adverse Events of Special Interest for the Coronavirus-Like Particle COVID-19 Vaccine

12.1.4.1.1 Vaccine-associated Enhanced Disease

Safety signal of VAED after exposure to MT-2766 will be closely monitored and assessed by retrieving data for this AESI as follows: AEs within the system organ class (SOC): immune system disorders and high level group term (HLGT): lower respiratory tract disorders (excluding obstruction and infection), cardiac disorders, signs and symptoms not elsewhere classified, vascular disorders, heart failures, arteriosclerosis, stenosis, vascular insufficiency and necrosis, cardiac arrhythmias, myocardial disorders, and vascular hemorrhagic disorders. High level term (HLT): renal failure and impairment and preferred term (PT): pericarditis, coagulopathy, deep vein thrombosis, pulmonary embolism, cerebrovascular accidents, peripheral ischemia, liver injury, Guillain-Barre syndrome, anosmia, ageusia, encephalitis, chilblains, vasculitis, erythema multiforme (based on standardized Medical Dictionary for Regulatory Activities (MedDRA®) classification) [Law 2020, Law 2020a] that require inpatient hospitalization (≥ 24 hours) and have laboratory confirmed SARS-CoV-2 infection will be monitored for assessment of any potential case of VAED. As this list can be updated during the study, any further changes to the AESI terms will be updated in the AESI list.

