APPENDIX 2 VAED

PT	PT Code
Asymptomatic COVID-19	10084459
Congenital COVID-19	10085080
Coronavirus infection	10051905
Coronavirus pneumonia	10084381
Coronavirus test positive	10070255
COVID-19	10084268
COVID-19 immunisation	10084457
COVID-19 pneumonia	10084380
COVID-19 prophylaxis	10084458
COVID-19 treatment	10084460
Exposure to SARS-CoV-2	10084456
Multisystem inflammatory syndrome	10086091
Multisystem inflammatory syndrome in adults	10085850
Multisystem inflammatory syndrome in children	10084767
Occupational exposure to SARS-CoV-2	10084394
Post-acute COVID-19 syndrome	10085503
SARS-CoV-2 antibody test positive	10084491
SARS-CoV-2 carrier	10084461
SARS-CoV-2 RNA decreased	10085496
SARS-CoV-2 RNA fluctuation	10085497
SARS-CoV-2 RNA increased	10085495
SARS-CoV-2 sepsis	10084639
SARS-CoV-2 test false negative	10084480
SARS-CoV-2 test positive	10084271
SARS-CoV-2 viraemia	10084640
Suspected COVID-19	10084451
Thrombosis with thrombocytopenia syndrome	10086158
Vaccine derived SARS-CoV-2 infection	10085492

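### The SAP's VAED list (Appendix 2) does not match the VAED criteria in SAP 7.1.3.1.3.1, and the SAP does not say which of the two fills the VED row

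*SAP*

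**What the plan says.** VAED is one of the three kinds of AESI named in primary safety endpoint 4 (protocol and SAP 2.2.1). SAP 8.3.2 gives it a row, labelled VED, in the overviews for the Day 0-21 periods and up to end of study, next to an overall AESI row. That section does not say how the VED row is derived.

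SAP 7.1.3.1.3.1 and protocol 12.1.4.1.1 describe the same retrieval: one SOC, several HLGTs, one HLT and 14 PTs, for events "that require inpatient hospitalization (≥ 24 hours) and have laboratory confirmed SARS-CoV-2 infection". Events found this way are to be assessed as potential cases.

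The SAP section closes with "VAED list is attached in the Appendix". Appendix 2, headed VAED, lists coded PTs. Most are coronavirus infection or test terms, and some are not infections at all, for example "Exposure to SARS-CoV-2" and "COVID-19 immunisation". It also holds "Suspected COVID-19". No hospitalisation or confirmation condition is attached to it.

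**The concern.** The SAP offers two sources for one AESI, and they disagree. A programmer has reason to pick either. The text gives a rule but no codes. The appendix has codes and the right title, and it is attached in the same way as the hypersensitivity and pIMD lists, where the appendix is the only itemised source. SAP section 1 puts the SAP above the protocol on analysis detail, so the protocol wording does not settle the matter.

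The choice matters because COVID-19 itself enters the AE data. Protocol 11.1.3 says "Confirmed COVID-19 cases will be recorded as AEs" and adds, for unconfirmed cases, "Any potential COVID-19 case that is not a confirmed event and does meet the criteria for an SAE will be reported". A VED row built from Appendix 2 would mostly count COVID-19, whether or not it was severe, under a label that signals harm from the vaccine. The overall AESI row would take in the same subjects.

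**Working it through.** The documents give no VAED rate to reproduce. The check compares the two sources and then follows individual subjects through each.

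**Inputs.** The 14 PTs and two conditions in SAP 7.1.3.1.3.1; the PTs in SAP Appendices 2, 3 and 4; planned group sizes of 100 (Group 1) and 25 (Group 2) from SAP 3.2. Group 3 was not enrolled (SAP 10).

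**Step 1: content of Appendix 2.** It has 28 PTs. Four are not coronavirus terms: three multisystem inflammatory syndrome PTs and thrombosis with thrombocytopenia syndrome. 28 − 4 = 24 coronavirus terms.

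**Step 2: overlap.** None of the 14 PTs named in the text is among the 28, so the overlap is 0 of 14. This is at PT level. Whether an Appendix 2 PT falls under a SOC or HLGT named in the text depends on the MedDRA hierarchy, which the documents do not give.

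**Step 3: the PTs that name the condition.** *Vaccine associated enhanced disease* and *Vaccine associated enhanced respiratory disease* are both absent from Appendix 2. Both are in Appendix 3 (hypersensitivity) and Appendix 4 (pIMD).

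**Step 4: the same subject under each source** (text rule with both conditions applied to every term level).

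| Subject's event | Text rule | Appendix 2 alone |
|---|---|---|
| Confirmed COVID-19, not hospitalised | not VED | VED |
| Unconfirmed case, coded as suspected COVID-19 | not VED | VED |
| Named organ event, hospitalised at least 24 h, confirmed infection also recorded as a COVID-19 AE | potential VAED | VED, but through the COVID-19 term |
| Event coded to a VAED PT | not a named PT | not VED; shown under pIMD, and under hypersensitivity if related |

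**Step 5: size per subject.** For the first line of the table, the VED row changes by 1 / group size:

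- Group 1: 1/100 = 1.0 percentage point
- Group 2: 1/25 = 4.0 percentage points
- Text rule with both conditions: 0 in either group

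The PT *COVID-19* is in neither Appendix 3 nor Appendix 4, so under the list such a subject enters the overall AESI row only because of Appendix 2. The fourfold difference between groups is the 4:1 allocation and says nothing about vaccine effect.

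**The case against.** The strongest reply is that the text already governs. It says what is retrieved and on what conditions, and the protocol agrees. On that reading the VED row is right and all that is missing is a linking sentence. Changes to the AESI terms are also referred to a Signal Management Plan, which is not among the documents and may explain the list. This is a natural reading, and it means that miscounting is possible, not established. It does not remove the conflict, because the SAP itself calls Appendix 2 the VAED list and gives no other derivation of the row.

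Several stronger readings are tempting and are not supported:

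- **That COVID-19 will be counted as VAED.** This holds only if Appendix 2 drives the flag.
- **That the share of odd terms in Appendix 2 measures misclassification.** Dictionary terms are not cases, and nothing in the plan records exposure or immunisation as AEs. Protocol 8.5.1 records COVID-19 vaccine as a concomitant medication.
- **That unconfirmed symptom reports will fill the row.** Protocol 9.3.15 collects reports of COVID-19 symptoms, but symptoms such as fever or cough are not Appendix 2 PTs. Confirmed COVID-19 is the main route.
- **That true enhanced disease would be lost.** A hospitalised organ event with confirmed infection would normally still flag the subject through the COVID-19 AE. An event coded to a VAED PT would miss the VED row but still reach the overall AESI row through Appendix 4.
- **That the hospitalisation and confirmation conditions reach only the HLT and PTs**, because a full stop precedes them ("and vascular hemorrhagic disorders. High level term (HLT): renal failure and impairment and preferred term (PT"). The words before the stop are a fragment of a list, and applying the conditions to all levels is the more natural reading. One clarifying phrase is enough.

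**Conclusion.** The concern holds as a conflict between two stated sources for a component of primary safety endpoint 4, and it should be fixed. The mismatch is certain: 0 of 14 named PTs shared, neither condition carried over, and both VAED PTs listed elsewhere.

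The effect on results is conditional. If Appendix 2 drives the flag, each non-hospitalised confirmed COVID-19 case adds 1.0 point to the Group 1 VED row or 4.0 points to the Group 2 row, against 0 under the text. This assumes the planned group sizes as denominators and both conditions applied to all term levels. The documents give no COVID-19 incidence, so no expected number of such cases, and no direction of any difference between groups, can be stated.

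A reader might infer that a primary safety test is compromised. It is not: these summaries are descriptive (SAP 8.3.1.3), AESIs are also tabulated by SOC and PT (SAP 8.3.2.2), and all safety data are listed (SAP 8.3). Cases can be traced, and no error rate or power is involved. What is at risk is the meaning of a headline safety row.

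**What to change.** In SAP 7.1.3.1.3.1:

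1. State that the VED row is derived from the text criteria, with the hospitalisation and laboratory-confirmation conditions applied to all listed term levels (SOC, HLGT, HLT and PT), and label the row *potential VAED*.
2. State that a match to Appendix 2 alone does not flag VED. Retitle the appendix, for example *COVID-19-related terms*, and state its role, such as helping to locate SARS-CoV-2 infection records subject to laboratory confirmation. Say separately how its terms that are not infection records are handled: exposure, immunisation, prophylaxis, the three multisystem inflammatory syndrome PTs, and thrombosis with thrombocytopenia syndrome. The last four are also in Appendix 4, so they stay within the AESI summaries in any case.
3. Show events coded to the two VAED PTs in the VED row, and state whether the two conditions apply to them.

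The cost is a few sentences, a new appendix title and reprogramming of one flag. Coded AEs, hospitalisation (through the SAE criteria) and COVID-19 confirmation are already collected. If the database is already locked, protocol 14.5 calls for the change and its reason to be given in the clinical study report.
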